### Type of Participant and Disease Characteristics:

2. Confirmed SARS-CoV-2 infection as determined by RT-PCR in any specimen collected within 5 days prior to randomization.

Note: RT-PCR is the preferred method; however, with evolving approaches to confirmation of SARS-CoV-2 infection, other molecular or antigen tests that detect viral RNA or protein are allowed. The test result must be available to confirm eligibility. Participants may be enrolled based on positive results of a rapid SARS-CoV-2 antigen test performed at screening.

- 3. Initial onset of signs/symptoms attributable to COVID-19 within 5 days prior to the day of randomization and at least 1 of the specified signs/symptoms attributable to COVID-19 present on the day of randomization (see Appendix 9 for criteria).
- 4. Has at least 1 characteristic or underlying medical condition associated with an increased risk of developing severe illness from COVID-19 including:
  - $\geq 60$  years of age;
  - BMI >25;
  - Current smoker (cigarette smoking within the past 30 days) and history of at least 100 lifetime cigarettes;
  - Immunosuppressive disease (eg, bone marrow or organ transplantation or primary immune deficiencies) OR prolonged use of immune-weakening medications:
    - Has received corticosteroids equivalent to prednisone ≥20 mg daily for at least 14 consecutive days within 30 days prior to study entry.
    - Has received treatment with biologics (eg, infliximab, ustekinumab), immunomodulators (eg, methotrexate, 6MP, azathioprine) or cancer chemotherapy within 90 days prior to study entry.
    - $\circ~$  HIV infection with CD4 cell count  ${<}200~mm^3$  and a viral load less than 400 copies/mL
  - Chronic lung disease (if asthma, requires daily prescribed therapy);
  - Known diagnosis of hypertension;
  - CVD, defined as history of any of the following: myocardial infarction, stroke, TIA, HF, angina with prescribed nitroglycerin, CABG, PCI, carotid endarterectomy, and aortic bypass;
  - Type 1 or Type 2 diabetes mellitus;
  - CKD provided the participant does not meet Exclusion Criterion 5;
  - Sickle cell disease;

- Neurodevelopmental disorders (eg, cerebral palsy, Down's syndrome) or other conditions that confer medical complexity (eg, genetic or metabolic syndromes and severe congenital anomalies);

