## 8.1.3. Daily Signs and Symptoms of COVID-19

On Day 1, participants will complete the study diary before receiving study intervention. Participant assessment of COVID-19-related symptoms should be recorded at approximately the same time each day as specified in the SoA and described in Section 8.1.1.

COVID-19-related symptoms will be evaluated in accordance with FDA guidelines (Appendix 10). Participants will record a daily severity rating of their symptom severity over the past 24 hours based on a 4-point scale in which 0 is reported if no symptoms were present; 1 if mild; 2 if moderate; and 3 if severe.

Vomiting and diarrhea will each be rated on a 4-point frequency scale where 0 is reported for no occurrence, 1 for 1 to 2 times, 2 for 3 to 4 times, and 3 for 5 or greater.

Sense of smell and sense of taste will each be rated on a 3-point Likert scale where 0 is reported if the sense of smell/taste was the same as usual, 1 if the sense of smell/taste was less than usual, and 2 for no sense of smell/taste.

Targeted COVID-19-associated symptoms are a subset of these symptoms (Appendix 9).

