### 9.3.3. Key Secondary Efficacy Endpoint(s)/Estimand(s) Analysis

# Proportion of participants with COVID-19 related hospitalization or death due to any cause through Day 28

The first key secondary efficacy endpoint is the proportion of participants with COVID-19 related hospitalization or death due to any cause through Day 28 in the mITT1 analysis set. The analysis for this endpoint is similar to the primary endpoint, but using the mITT1 analysis set.

# Time to sustained alleviation and time to sustained resolution of targeted COVID-19 sign/symptoms through Day 28

The key secondary endpoints of sustained alleviation and resolution will be defined for all targeted COVID-19 associated symptoms based on self-assessment.

Sustained alleviation of all targeted COVID-19 signs/symptoms is defined as the event occurring on the first of 4 consecutive days when all symptoms scored as moderate or severe at study entry are scored as mild or absent AND all symptoms scored mild or absent at study entry are scored as absent. The first day of the 4 consecutive-day period will be considered the First Event Date.

Sustained resolution is defined as when all targeted symptoms are scored as absent for 4 consecutive days. The first day of the 4 consecutive-day period will be considered the First Event Date.

For any symptoms not present at baseline, it must be absent at the last possible available day (prior to or at Day 25) to be counted as sustained alleviation/resolution. For symptoms with no reported severity in baseline, the symptom will have to be absent in order to consider alleviated/resolved (missing severity at baseline will be treated as mild).

Day 25 is the last possible day the symptom alleviation and resolution endpoints can be achieved (definition includes data from the subsequent three days) and Day 28 is the last day participants report their daily signs and symptoms.

The time to sustained symptom alleviation/resolution for the purpose of this study is defined as:

- For a participant with sustained symptom alleviation/resolution (event), time to event will be calculated as (First Event Date) (First Dose Date) +1.

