## 10.9. Appendix 9: Signs and Symptoms Attributable to COVID-19

## Table 2. Signs and Symptoms Attributable to COVID-19

Daily Sign and Symptom Collection 	Entry Criterion#3 Targeted (used for study entry)	Daily Signs and Symptom Collection	Targeted Symptoms For Analysis
Cough	X	X	X
Shortness of breath or difficulty breathing	X	X	X
Fever (documented temperature >38°C [100.4°F]) or subjective fever (eg, feeling feverish)	X		
Feeling feverish		Х	X
Chills or shivering	Х	X	X
Fatigue (low energy or tiredness)	Х	X	
Muscle or body aches	Х	X	X
Diarrhea (loose or watery stools)	Х	X	X
Nausea (feeling like you wanted to throw up)	Х	X	X
Vomiting (throw up)	Х	X	X
Headache	Х	X	X
Sore throat	Х	X	X
Stuffy or runny nose	X	X	X
Loss of smell		X	
Loss of taste		X	

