6.2.3. Incidence of SAEs and AEs Leading to Discontinuations

The incidence of SAEs and AEs leading to discontinuation will be summarized by treatment group using the SAS population.

6.2.4. Time (days) to Sustained Alleviation and Time to Resolution of Targeted COVID-19 Sign/Symptoms through Day 28

The time (days) to sustained alleviation and time to resolution will be defined for all targeted COVID-19 associated symptoms based on self-assessment.

Sustained alleviation of all targeted COVID-19 signs/symptoms is defined as the event occurring on the first of 4 consecutive days when all symptoms scored as moderate or severe at study entry are scored as mild or absent AND all symptoms scored mild or absent at study entry are scored as absent. The first day of the 4 consecutive-day period will be considered the First Event Date.

Sustained resolution is defined as when all targeted symptoms are scored as absent for 4 consecutive days. The first day of the 4 consecutive-day period will be considered the First Event Date.

For symptoms with no reported severity in baseline, the symptom will have to be absent in order to be counted as sustained alleviated/resolved (missing severity at baseline will be treated as mild).

Day 25 is the last possible day the symptom alleviation and resolution endpoints can be achieved (definition includes data from the subsequent three days) and Day 28 is the last day participants report their daily signs and symptoms.

The time to sustained symptom alleviation/resolution for the purpose of this study is defined as:

PFIZER CONFIDENTIAL
Page 23

- For a participant with sustained symptom alleviation/resolution (event), time to event will be calculated as (First Event Date) (First Dose Date) +1.
- For a participant that either completes Day 28 of the study or discontinues from the study before Day 28 without sustained symptom alleviation/resolution (censored), censoring date will be at the last date on which symptom alleviation/resolution is assessed, and time will be calculated as (Censoring Date) (First Dose Date) +1 or Day 25 whichever occurs first.

The decision to require 4 consecutive days with all targeted symptoms absent was based on exploratory analyses of data from the ACTIV-2/A5401 study, which suggested that this choice (rather than requiring fewer consecutive days) better captured sustained symptom resolution with low probability of subsequent relapse.

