- 1. Proportion of participants with any severe targeted signs/symptoms attributed to COVID-19 at DAY 1 (baseline).
- 2. Proportion of participants with any severe targeted signs/symptoms attributed to COVID-19 Day 2 to Day 6 (during treatment).
- 3. Proportion of participants with any severe targeted signs/symptoms attributed to COVID-19 Day 7 to Day 28 (post treatment).

Treatment comparison between the group will be presented as odds ratio and 95% CI using logistic regression with a similar analysis model as specified in Section 6.1.1.2. The analyses will be done using mITT, mITT1, and mITT2 populations.

In the mITT population, the analysis will be repeated in subgroups based on baseline serology status (positive, negative), by baseline viral load ($<10^4$ copies/mL, $\ge10^4$ copies/mL) and ($<10^7$ copies/mL, $\ge10^7$ copies/mL).

An additional follow-up analysis for signs/symptoms data will be conducted at Week 12 and Week 24 for all signs/symptoms (not just targeted signs/symptoms, See Appendix 5). The Week 12 and Week 24 signs/symptoms data is collected from a long-term FU telemedicine interview performed by the site to participant and collected in CRF (diary data is not colected after Day 34).

The observed proportion of participants with any mild, moderate, and severe of all signs/symptoms attributed to COVID-19 at Week 12 and Week 24 will be summarized by treatment group and overall. Observed proportion of participants reporting the presence of each sign and symptom that is mild, moderate, or severe categories will also be summarized by treatment group and overall.

The analyses will be done using mITT, mITT1, and mITT2 populations.

6.2.6. Duration of Each Targeted COVID-19 Sign/Symptom through Day 28

Duration of each targeted COVID -19 signs/symptoms is defined as (First Date when the symptom alleviated/resolved) – (First Dose Date) +1 for each participant with baseline severity of mild, moderate or severe.

PFIZER CONFIDENTIAL
Page 25

Duration of each targeted COVID-19 sign/symptom with a mild or worse severity will be summarized for each group within mITT, mITT1, and mITT2 populations.

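### Fatigue alone qualifies for entry but is not a targeted symptom, so some participants with nothing to alleviate can be scored as alleviated and resolved at Day 1

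*SAP*

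**What the plan says.** **Entry.** Protocol 5.1, criterion 3, asks for "at least 1 of the specified signs/symptoms attributable to COVID-19 present on the day of randomization". In protocol Appendix 9, Table 2, the row that begins "Fatigue (low energy or tiredness" is marked for entry and for daily collection, but not for targeted analysis. SAP Appendix 5 marks it the same way.

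**Endpoint.** SAP 6.2.4 says that alleviation and resolution "will be defined for all targeted COVID-19 associated symptoms based on self-assessment". For alleviation, symptoms moderate or severe at entry must become mild or absent, and "all symptoms scored mild or absent at study entry are scored as absent", on 4 consecutive days. For resolution, protocol 9.3.3 states: "Sustained resolution is defined as when all targeted symptoms are scored as absent for 4 consecutive days". In both cases, "The first day of the 4 consecutive-day period will be considered the First Event Date", and time is that date minus the first dose date plus 1. Missing baseline severity counts as mild. Participants hospitalized for COVID-19 or dying within 28 days are classed as not achieving the endpoint and are censored at Day 25.

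**Timing.** The protocol Schedule of Activities makes Day 1 the start of dosing. Protocol 8.1.3 adds: "On Day 1, participants will complete the study diary before receiving study intervention".

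**Where the texts differ.** Protocol 9.3.3 says that a symptom not present at baseline must also be absent on the last available day up to Day 25. SAP 6.2.4 does not repeat this. For single-symptom durations, SAP 6.2.6 does set a baseline condition: "for each participant with baseline severity of mild, moderate or severe".

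**The concern.** The entry list and the endpoint list do not match, and nothing in the endpoint definition bridges the gap. A participant enrolled on fatigue alone can score every targeted symptom absent before the first dose. For that person the alleviation and resolution rules become the same: stay free of targeted symptoms for 4 days. Nothing has to improve.

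This matters because time to sustained alleviation is tested in sequence after the primary endpoint (protocol 9.1, SAP 5.1), and time to resolution belongs to the SAP's Hochberg family. Successes that reflect no improvement weaken the contrast in both. SAP 5.1 also says that alleviation is tested before hospitalization or death in mITT1, although both documents list that endpoint first. If the SAP sentence governs, a failed alleviation test would also block formal testing of that endpoint. The order is a separate conflict to settle.

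**Working it through.** **1. The plan's own figure.** A 4-day run must end by Day 28, so the last possible event day is 28 - 4 + 1 = 25. This agrees with both documents.

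**2. The lists compared.** Table 2 has 12 entry items and 11 targeted items. Two entry items are not targeted: fatigue, and fever as worded for entry (documented temperature or subjective fever). The targeted list has feeling feverish instead. The fever route is narrow, because the entry item includes feeling feverish and the diary covers the past 24 hours. Fatigue is the main route.

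**3. The rule applied to constructed diaries**, with the Day 1 diary as baseline:

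| Targeted symptoms | Event day |
|---|---|
| None on any day | 1 (time = 1 - 1 + 1 = 1) |
| None on Day 1; mild cough on Day 3 only | 4 |
| None on Day 1; cough on Days 3-10 | 11 |
| None until cough from Day 20 onward | 1 under the SAP; no event under the protocol's last-day rule |
| One missing on Day 1 (treated as mild), then all absent | 2 |
| One present on Day 1 only, mild or moderate | 2 |

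A symptom that is mild on Day 1 is not absent that day, and one that is moderate or severe is not mild or absent. So a Day 1 event can come only from a participant with no targeted symptom at baseline, but not every such participant has one.

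**4. Size.** The documents do not say how many participants would have a Day 1 event. Assumptions:
- share f with such an event, equal in both arms: 2%, 5% or 10%
- exponential times in the rest, placebo median 14 days, true hazard ratio (HR) 1.25
- 24 days at risk (Day 1 to Day 25)
- n = 1717, the planned primary-analysis number

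Proportion with an event among the rest:
- placebo: 1 - 2^(-24/14) = 0.695
- active: 1 - 2^(-1.25 × 24/14) = 0.774
- average: 0.734

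Formulas:
- Day 1 share of all events: s = f / (f + (1 - f) × 0.734)
- diluted HR: exp((1 - s) × ln 1.25), since Day 1 events split evenly carry no treatment contrast
- median: solve (1 - f) × S(t) = 0.5, so placebo = 14 × log2(2(1 - f)), and active = placebo / 1.25
- power: Φ(ln(diluted HR) × √(D/4) - 1.96), with D = 1717 × (f + (1 - f) × 0.734)

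| f | s | HR | Placebo median | Active median | Difference | Power |
|---|---|---|---|---|---|---|
| 0 | 0 | 1.25 | 14.0 | 11.2 | 2.80 | 98% |
| 2% | 2.7% | 1.24 | 13.6 | 10.9 | 2.72 | 97% |
| 5% | 6.7% | 1.23 | 13.0 | 10.4 | 2.59 | 96% |
| 10% | 13.1% | 1.21 | 11.9 | 9.5 | 2.37 | 94% |

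Cox simulations under the same assumptions agree to within about 0.01 in the HR. With a true HR of 1.20, the same formulas give an HR of about 1.19, 1.19 and 1.17, and power falls from 90% to 88%, 86% and 81%.

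**The case against.** The strongest reply is that the effect is small, of unknown frequency, and conservative. That stands. The table is also an upper bound if f is read as the share with no targeted symptom at baseline, because only those who stay clear on Days 1-4 get the Day 1 event.

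Three stronger readings are tempting, and the documents do not support them:
- *Everyone without a targeted symptom at baseline is a Day 1 success.* A targeted symptom on Days 2-4 moves the event later. COVID-19 hospitalization or death through Day 28 removes it. The protocol's last-day rule removes some others.
- *The event is settled before the drug can act.* Only the event date precedes treatment. Days 2-4 are on treatment and help decide whether the event occurs, so equal frequency in the arms is an expectation, not a certainty.
- *The damage is the fall in the placebo median, about 1 day at 5% and 2 days at 10%.* The estimand is the difference in medians, and both medians fall. The loss is about 0.1 to 0.4 days.

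A further objection is that the secondary estimand (protocol 9.1.1.2, SAP 2.1.2) covers all nonhospitalized patients at increased risk, so a restriction changes its population. That is right, and the estimand has to be amended with the analysis. SAP 6.2.6 is only a partial precedent, since the duration of one symptom presupposes that the symptom is present.

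**Conclusion.** The gap is real and can be read directly from the definitions: some participants with no targeted symptom to alleviate will count as successes at time 1 in a sequentially tested endpoint and in a Hochberg-tested one. The expected consequence is mild conservative dilution, not bias toward either arm. It is negligible if about 2% of participants have such events. It is modest at 5-10%, where an HR of 1.25 becomes 1.23 to 1.21 and the difference in medians loses 0.2 to 0.4 days. These sizes rest on the assumed share, the 14-day placebo median, exponential times and equal frequency in the arms; none of these comes from the documents. The primary endpoint is not affected.

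**What to change.** - In SAP 6.2.4, SAP Appendix 1 and protocol 9.3.3, restrict the alleviation and resolution analyses to participants with at least one targeted symptom of mild or worse severity at baseline, with missing baseline severity still treated as mild. By step 3 of the working, this removes every Day 1 event.
- Amend the secondary estimand population in protocol 9.1.1.2 and SAP 2.1.2 to match.
- Report the number excluded by arm, and keep the unrestricted analysis as a sensitivity analysis.
- Reconcile SAP 6.2.4 with the protocol 9.3.3 rule that a symptom not present at baseline must be absent on the last available day. At present the two texts can score the same diary differently.

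The cost is a few sentences, a slightly smaller n for two secondary endpoints and a slightly narrower estimand population. The filter uses a pre-dose variable, so the randomized comparison is kept.

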3.5. Stratification Variables

Randomization will be stratified by geographic region and whether participants had received or were expected to receive COVID-19 therapeutic mAb treatment (yes/no) based on the site investigator's assessment at the time of randomization. Randomization for the strata where participants had received or were expected to receive COVID-19 therapeutic mAb treatment will be capped at a maximum of 25% enrollment. Unless otherwise indicated analyses will include calculated values for quantitative stratification variables. Geographical region is defined as follows:

- US region: country of the United States, including Puerto Rico.
- Europe region: countries of Bulgaria, Czech Republic, Hungary, Netherlands, Poland, Spain, and Ukraine.
- Brazil region: country of Brazil.
- India region: country of India.
- Rest of the World region: countries of Argentina, Colombia, Japan, Malaysia, Mexico, Peru, Russian Federation, South Africa, Republic of Korea, Taiwan, Thailand, and Turkey.

If a region enrolled <10 participants, the region will be combined with the "rest f the word" region.

Baseline and stratification variables above defined will be applied to the analyses depending on the analysis population used:

- mITT analyses will include the following stratification variables: Baseline viral load, baseline serology status, geographic region.
- mITT1 analysis will include: Baseline viral load, baseline serology status, geographic region and symptom onset days to first dose date (≤3 days, >3 days).
- mITT2 analyses will include: Baseline viral load, baseline serology status, geographic region, received or were expected to receive mAb treatment (yes/no) and symptom onset days to first dose date (≤3 days, >3 days).

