Participants who are hospitalized for the treatment of COVID-19 or death from any cause during the 28-day period will be classified as not achieving sustained symptom alleviation/resolution and will be censored at day 25.

Cox proportional hazard model analyses will be used for time to sustained symptom alleviation/resolution. Cox proportional hazard model will include treatment and region effect as independent variables. In addition, the stratification variables specified in Section 3.5 will be added to the model analyses depending of the analysis population.

Time to sustained symptom alleviation/resolution will be summarized graphically using Kaplan-Meier plots for each of the treatment groups, the analyses will be done using the mITT population only.

In the mITT populations, the analysis will be repeated in subgroups based on baseline serology status (positive, negative), by baseline viral load ($<10^4$ copies/mL, $\ge 10^4$ copies/mL), and ($<10^7$ copies/mL, $\ge 10^7$ copies/mL).

6.2.5. Proportion of Participants with Severe Signs/Symptoms Attributed to COVID-19 through Day 28

Participants will record a daily severity rating of their symptom severity over the past 24 hours based on a 4-point scale in which 0 is reported if no symptoms were present; 1 if mild; 2 if moderate; and 3 if severe.

Vomiting and diarrhea will each be rated on a 4-point frequency scale where 0 is reported for no occurrence, 1 for 1 to 2 times, 2 for 3 to 4 times, and 3 for 5 or greater. Sense of smell and sense of taste will each be rated on a 3-point Likert scale where 0 is reported if the sense of smell/taste was the same as usual, 1 if the sense of smell/taste was less than usual, and 2 for no sense of smell/taste.

The proportion of participants with any severe targeted signs/symptoms attributed to COVID-19 through Day 28 will be summarized by treatment group. A participant with severe score for any targeted symptoms post-baseline will be counted as severe. Proportions for each targeted signs and symptom with severe category only will be plotted over time through Day 28. Additionally, the proportion of participants reporting the presence of each targeted sign and symptom that is mild, moderate or severe categories will also be presented. In addition, to understand the severity of signs/symptoms attributed to COVId-19, the following analysis will be performed:

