Appendix 2. Data Derivation Details

Appendix 2.1. Definition and Use of Visit Windows in Reporting

Visit Number	Visit Label	Definition [Day window]		
2	Baseline	= Day -2 to Day 1		
3	Day 3	= Day 3, with a window of ±1 days, (ie, days 2 to 4)		
4	Day 5	= Day 5, with a window of ±1 days, (ie, days 4 to 6)		
5	Day 10	= Day 10, with a window from days 7 to 11		
6	Day 14	= Day 14, with a window from days 12 to 17		
7	Day 21	= Day 21, with a window from 18 to 24		
8	Day 34	= Day 34, with a window from days 25 to 37		
9	Week 12	= Day 84, with a window of ±7 days, (ie, days 77 to 91)		
10	Week 24	= day 168 with a window of ±7 days, (ie, days 161 to 175)		

The following table defines the visit windows and labels to be used for reporting:

- Viral load: Baseline visit is set up according to study days of Day -2 to Day 1. The only viral load results collected after the start of dosing during the Baseline visit that are treated as Baseline data are those that were collected within 1 hour post start of dosing.
- Labs, COVID-19 Signs and Symptoms, Vital Signs and ECG: Baseline window will be Day -2 to Day 1, without any consideration to the time factor.
- When data from study Day 4 has an overlap between Day 3 and Day 5 windows, decision made is to assign the window according to the nominal visit. The rule will not be applicable to other study days 2 and 3 for Day 3 window, and days 5 and 6 for Day 5 window.
- If multiple readings fall into the same window, choose the one closer to the target day. If equidistant, then select the later one after the target day.
- Sign and symptom data at Week 12 & Week 24: No visit windowing will be applied. The nominal visits will be used.

Abbreviation	Term
AE	adverse event
AESI	adverse events of special interest
ANCOVA	analysis of covariance
BOCF	baseline observation carried forward
CDARS	Clinical Data Analysis and Reporting System
CI	confidence interval
ECG	electrocardiogram
E-DMC	external data monitoring committee
ET	early termination
FAS	full analysis set
FDA	Food and Drug Administration (United States)
LOCF	last observation carried forward
MedDRA	Medical Dictionary for Regulatory Activities
ITT	intent-to-treat
MMRM	mixed-effects model with repeated measures
PD	pharmacodynamic(s)
PK	pharmacokinetic(s)
PP	per-protocol
PT	preferred term
QTc	corrected QT
QTcF	corrected QT (Fridericia method)
SAE	serious adverse event
SAP	statistical analysis plan
SAS	Safety Analysis Set
SD	standard deviation
SOC	Schedule of Activities

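### The severe-symptom comparison in SAP 6.2.5 does not separate severe symptoms persisting from entry from new ones, and its model omits baseline symptom severity

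*SAP*

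**What the plan says.** **Event.** SAP 6.2.5 makes a participant an event on one post-baseline score: "A participant with severe score for any targeted symptoms post-baseline will be counted as severe". SAP Appendix 2.1 fixes the symptom baseline: "Baseline window will be Day -2 to Day 1, without any consideration to the time factor". Day 2 is thus the first post-baseline day.

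**Windows.** SAP 6.2.5 also asks for the severe proportion on Day 1, over Days 2 to 6 and over Days 7 to 28.

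**Model.** The comparison is an odds ratio with 95% CI from a logistic model similar to that in SAP 6.1.1.2: treatment and region plus the SAP 3.5 variables. For the primary population, "mITT analyses will include the following stratification variables: Baseline viral load, baseline serology status, geographic region". The mITT1 set adds time from symptom onset, and mITT2 adds onset and antibody status. Further covariates may be added if necessary, with age and gender as examples. SAP 5.2.1 also describes a difference in proportions for this endpoint, and Appendix 1 lists Kaplan-Meier beside logistic regression. None of these texts uses baseline severity.

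**Diary.** Protocol 8.1.3 says: "On Day 1, participants will complete the study diary before receiving study intervention". Baseline severity is therefore collected before dosing.

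**Missing data.** SAP 5.3 and Appendix 1 apply baseline or last observation carried forward (BOCF/LOCF) to this endpoint. The mITT definition in SAP 4 does not require a post-baseline visit, whereas Protocol 9.2 does.

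**The concern.** Protocol 5.1 requires at least one symptom on the day of randomization, so everyone enters symptomatic and some may be severe on Day 1. If those participants tend to record another severe score, Day 1 status explains much of the outcome in both arms. A model without it leaves that variation unexplained.

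Two things are at stake. The treatment test is weaker than the collected data allow. The reported odds ratio also mixes persistence of severe symptoms with their emergence, so a reader cannot tell which the treatment affected.

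The carry-forward rule adds a smaller ambiguity. Read literally, a severe Day 1 score in someone with no later diary entry could be imputed to post-baseline days and counted as an event that nobody observed.

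Other endpoints do use the starting value. Alleviation (SAP 6.2.4) and worsening (6.2.7) are defined against baseline, oxygen saturation (6.2.8) is cross-tabulated by Day 1 status, and the viral-load models (6.2.11) adjust for baseline.

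**Working it through.** **The plan's own figure.** The documents state no event rate, effect or power for this endpoint. The only relevant figure is the primary-endpoint size of 1717 (Protocol 9.5), used here only to supply N. With 7% versus 3.5%, two-sided 5% and 90% power:

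n per arm = [1.96 √(2 × 0.0525 × 0.9475) + 1.2816 √(0.07 × 0.93 + 0.035 × 0.965)]² / 0.035² = 852

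That is 1704 in total, close to 1717. Half of 1717 is 858 per arm, rounded down.

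**Assumed inputs (none is in the documents).**
- b, the share severe on Day 1: 15, 25 or 35%.
- Later severe score in placebo participants severe on Day 1: 90%.
- Newly severe among the rest: 20% placebo, 15% active, so OR = (0.15/0.85)/(0.20/0.80) = 0.71.
- Scenario A: no effect in those severe at entry (90% in both arms).
- Scenario B: the same OR of 0.71 in those severe at entry. Odds 9 × 0.706 = 6.35, which gives 86.4% on active.

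**Unadjusted, worked for b = 25%, scenario A.**
- Placebo: 0.25 × 0.90 + 0.75 × 0.20 = 37.5%. Active: 0.25 × 0.90 + 0.75 × 0.15 = 33.75%.
- OR = (0.3375/0.6625)/(0.375/0.625) = 0.85, log OR = −0.164.
- SE = √[1/(858 × 0.375 × 0.625) + 1/(858 × 0.3375 × 0.6625)] = 0.101.
- Power = Φ(0.164/0.101 − 1.96) = 37%.

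**Adjusted for Day 1 status, same case.** Combining the two strata by inverse variance closely approximates the logistic fit.
- Not severe, 643.5 per arm: log OR −0.348, variance 1/(643.5 × 0.16) + 1/(643.5 × 0.1275) = 0.0219, weight 45.7.
- Severe, 214.5 per arm: log OR 0, variance 2/(214.5 × 0.09) = 0.1036, weight 9.65.
- Pooled log OR = −0.348 × 45.7/55.3 = −0.288 (OR 0.75), SE = 1/√55.3 = 0.134.
- Power = Φ(2.14 − 1.96) = 57%.

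**All cases (logistic model fitted to expected counts).**

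| Scenario | Severe at entry | Unadjusted OR | Power | Adjusted OR | Power |
|---|---|---|---|---|---|
| A: no effect in those severe at entry | 15% | 0.81 | 50% | 0.73 | 66% |
| A | 25% | 0.85 | 37% | 0.75 | 57% |
| A | 35% | 0.88 | 27% | 0.77 | 48% |
| B: same OR in both groups | 15% | 0.79 | 60% | 0.71 | 76% |
| B | 25% | 0.82 | 52% | 0.71 | 75% |
| B | 35% | 0.83 | 47% | 0.71 | 73% |

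The SE of the log odds ratio is larger after adjustment (0.134 against 0.101 in the worked case), but the log odds ratio grows more. The gain is in the test statistic. In B the whole shift from 0.71 is non-collapsibility: nothing is biased, and the two odds ratios answer different questions. In A part of the shift reflects a real lack of effect in one group.

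**Sensitivity to persistence.** Take new severe rates of 20% versus 10% (OR 0.44), with 10 to 50% severe at entry. With no effect in that group, the unadjusted OR is 0.51 to 0.75 at 30% persistence and 0.59 to 0.82 at 90%. With a common OR of 0.44 it is 0.47 to 0.50 at 60% persistence and 0.55 to 0.67 at 90%; the risk difference is then 10 to 15 points, not below the 10 points among those not severe at entry.

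**The case against.** **Persistence belongs to the endpoint.** The protocol objective covers duration as well as severity of symptoms, and clearing severe symptoms sooner is a benefit. This stands. It argues against redefining the event as new severity only, but not against a covariate.

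**The plan already looks at baseline.** SAP 6.2.7 analyses worsening relative to baseline, and SAP 6.2.5 tabulates Day 1 and separates Days 7 to 28. This mitigates part of the problem. However, worsening also counts non-severe changes, and nothing in 6.2.5 adjusts the windowed comparisons for Day 1 severity.

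**The optional covariates are open-ended.** They do not exclude baseline severity, but they do not commit to it either.

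**The endpoint carries little weight.** It is outside the three endpoints that SAP 5.1 lists for Hochberg testing, although Protocol 9.1 sends other secondary endpoints there without naming them. This stands and limits the consequence.

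**Stronger readings that the documents do not support.** A reader might infer that the 24-hour recall makes the Day 2 entry a report of pre-dose severity. Protocol 8.1.3 places the Day 1 entry before dosing and says that "symptoms should be recorded at approximately the same time each day as specified in the SoA". Day 2 recall therefore reaches back to about the Day 1 entry, and the overlap is only the gap to the first dose plus any drift in clock time. Nor is a severe Day 1 score an event by itself, since a post-baseline score is required. A reader might also infer that chance imbalance at baseline would be taken for a drug effect. Allocation is randomized 1:1, the test is valid under no effect, and the Day 1 table would show an imbalance.

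**Conclusion.** The omission is clear from the text. The event definition and model ignore a pre-dose measurement that is likely to predict the outcome strongly, so persistent and new severe symptoms are not separated. Validity under no effect is intact. What is lost is power, and the reported odds ratio sits nearer 1 than the baseline-adjusted one.

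The size cannot be fixed from the documents. In the main illustration, adjustment adds 16 to 21 percentage points of power if those severe at entry gain nothing (66 − 50 up to 48 − 27), and 16 to 26 if the odds ratio is equal (76 − 60 up to 73 − 47). These rest on the assumed 90% persistence and the assumed rates.

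It would go too far to say that the treatment effect is diluted as a matter of fact. That depends on the baseline share, on persistence, on the effect in those severe at entry and on the scale: part of the odds-ratio shift is non-collapsibility, and the risk difference need not shrink. The point concerns a supportive secondary endpoint and does not touch the primary conclusion.

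**What to change.** In SAP 6.2.5:

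1. Add any severe targeted symptom on the pre-dose Day 1 diary (yes/no) to the logistic model, for the overall endpoint and for the Day 2 to 6 and Day 7 to 28 windows. Missing baseline stays mild under SAP 5.3, so it counts as no.
2. Report results by Day 1 severe status as a supportive table, so that persistent and new severity can be read separately. Keep the event definition.
3. State that a baseline score carried forward under BOCF/LOCF does not by itself create a post-baseline severe event.

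The cost is SAP wording, one covariate already collected and one table, with no new data. The adjusted odds ratio is conditional on Day 1 severity and should be labelled so.
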